## **5.3. Lifestyle considerations**

### **5.3.1. Meals and dietary restrictions**

No restrictions.

### **5.3.2. Caffeine, alcohol, and tobacco**

- Participants will abstain from ingesting caffeine- or xanthine-containing products (e.g., coffee, tea, cola drinks, and chocolate) for 2 hours before the start of dosing until 1 hour after dosing.
- Participants will abstain from alcohol for 24 hours before admission until discharge from the clinical unit.
- Use of tobacco- and nicotine-containing products is not allowed from 6 months prior to screening until after the final follow-up visit.

### **5.3.3. Activity**

- Participants will abstain from strenuous exercise (exertion requiring maximum physical effort/strength) for 48 hours before each blood collection for clinical laboratory tests. Participants may participate in light recreational activities during the study (e.g., watching television, reading).

### **5.3.4. Other restrictions**

Participants will be asked to refrain from donating blood for the duration of their study participation.

## **5.4. Screen failures**

Screen failures are defined as participants who consent to participate in the clinical study but are not subsequently entered in the study. A minimal set of screen failure information is required to ensure transparent reporting of screen failure participants to meet the Consolidated Standards of Reporting Trials (CONSORT) publishing requirements and to respond to queries from regulatory authorities. Minimal information includes demography, screen failure details, eligibility criteria, any protocol deviations, and any SAEs.

Individuals who do not meet the criteria for participation in this study (screen failure) may not be rescreened unless discussed and agreed with the Medical Monitor. Individuals who fall out of the screening window, may be rescreened at the discretion of the investigator.

## **5.5. Criteria for temporarily delaying**

Not applicable.

CONFIDENTIAL

219239  
Protocol

## 6. STUDY INTERVENTION(S) AND CONCOMITANT THERAPY

Study intervention is defined as any investigational intervention(s), marketed product(s), placebo, or medical device(s) intended to be administered to a study participant according to the study protocol, and further details in [Table 5](#).

### 6.1. Study intervention(s) administered

**Table 5** Study Intervention(s) Administered

Intervention Label	Open Label	Open Label
Intervention Name	Bepirovirsen, (GSK3228836)	Bepirovirsen, (GSK3228836)
Intervention Description	Bepirovirsen solution for injection, CCI mg/mL packaged in a vial. CCI ██████████ required to deliver CCI mg dose.	Bepirovirsen solution for injection, CCI mg/mL packaged in a PFS fitted with a PFS SSD. CCI ██████████ required to deliver CCI mg dose.
Type	Drug	Drug
Dose Formulation	Solution for injection	Solution for injection
Unit Dose Strength(s)	CCI mg/mL	CCI mg/mL
Dosage Level(s)	CCI mg	CCI mg
Route of Administration	SC Injection	SC Injection
Use	Experimental	Experimental
IMP and NIMP/AxMP.	IMP	IMP
Sourcing	Supplied by GSK	Supplied by GSK
Packaging and Labeling	Study intervention will be provided in a carton with an insert. Each carton will be labeled as required per country requirement.	Study intervention will be provided in carton with an insert. Each carton will be labeled as required per country requirement.

Bepirovirsen Solution for Injection, **CCI** mg/mL, is a clear, **CCI** **██████████** solution, essentially free from visible particles. Bepirovirsen vial is presented as a 1 mL nominal fill volume of Bepirovirsen Solution for Injection **CCI** mg/mL in a **CCI** mL clear glass vial, closed with a **CCI** **██████████** rubber stopper and sealed with aluminium overseal with removeable plastic cap.

The drug product is administered as **CCI** SC injections to deliver the clinical dose of **CCI** mg. It is recommended to use 27G thin-wall needles or 25G regular-walled needles for injection.

The PFS SSD is a medical device and is described in Section [6.1.1](#).

**CONFIDENTIAL**219239  
Protocol

### 6.1.1. Medical devices

Bepirovirsen PFS SSD is a single use, prefilled, disposable device intended to enable manual delivery of the drug product while providing a needle shielding feature (post-use) and enhanced ergonomics. **CCI** [REDACTED]

[REDACTED]

[REDACTED]

[REDACTED]

[REDACTED]

**CCI** [REDACTED]**CCI** [REDACTED]

- Instructions for medical device use are provided **CCI** [REDACTED]
- All device deficiencies (including malfunction, use error and inadequate labeling) shall be documented and reported by the investigator throughout the clinical investigation (see Section 8.4.7 and Section 10.6) and appropriately managed by GSK.

### 6.2. Preparation, handling, storage, and accountability

- The investigator or designee must confirm appropriate conditions (e.g., temperature) have been maintained during transit for all study intervention received, and any discrepancies are reported and resolved before use of the study intervention.
- Only participants enrolled in the study may receive study intervention, and only authorized site staff or HCP may supply, prepare, or administer study intervention (see Section 4.1).
- All study intervention must be stored in a secure, environmentally controlled, and monitored (manual or automated) area in accordance with the labeled storage conditions with access limited to the investigator and authorized site staff.

**CONFIDENTIAL**219239  
Protocol

- The investigator, institution, the head of the medical institution (where applicable), or authorized site staff is responsible for study intervention accountability, reconciliation, and record maintenance (i.e., receipt, reconciliation, and final disposition records).
- Further guidance and information for the final disposition of unused study interventions are provided in the pharmacy manual.
- Under normal conditions of handling and administration, study intervention is not expected to pose significant safety risks to site staff. Take adequate precautions to avoid direct eye or skin contact and the generation of aerosols or mists. In the case of unintentional occupational exposure notify the monitor, Medical Monitor and/or GSK study contact.
- A Material Safety Data Sheet (MSDS)/equivalent document describing occupational hazards and recommended handling precautions either will be provided to the investigator, where this is required by local laws, or is available upon request from GSK.

### **6.3. Assignment to study intervention**

Study intervention will be dispensed on Day 1 as summarized in the SoA (Section 1.3).

The GSK Randomization Officer will use the Randall NG system to generate a randomization schedule.

With central randomization, knowledge of the randomized treatment group for previous participants does not predict which treatment group will be assigned to the next randomized participant.

Randomization and study intervention assignment will be facilitated by the IRT through the central RAMOS NG system.

Following confirmation of fulfilment of study entry criteria, study site personnel will be required to register participants using RAMOS NG for assignment of a unique identifier which comprises of 4 digits (e.g., 1 001 and increasing) designating each participant's randomization code and treatment sequence assignment.

Prior to first dosing of each group, participants will be assigned a unique number (randomization number) in ascending numerical order. The randomization number encodes the participant's assignment to one of the 4 treatment sequences of the study, according to the randomization schedule.

### **6.4. Randomization**

This is an open-label study; Any potential for selection bias will be reduced by central randomization.

A single randomization schedule will randomly assign participants pre-dose to treatment group and injection site according to the ratios shown in [Table 6](#).

CONFIDENTIAL

219239  
Protocol

Additionally, randomization will be stratified by body weight (CCI [REDACTED]  
[REDACTED]).

**Table 6 Randomization Schedule**

Group	Arm	Injection Site		Total
		Thigh	Abdomen	
1	1	1	1	3
2	1	1	1	3
3		1	1	2
4		1	1	2

## 6.5. Study intervention compliance

All participants will be dosed at the clinical site, where they will receive study intervention directly from the investigator or designee, or they will self-administer the medication provided, under medical supervision. The date and time of each dose administered in the clinic will be recorded in the source documents. The dose of study intervention and study participant identification will be confirmed at the time of dosing by a member of the study site staff other than the person administering the study intervention.

## 6.6. Dose modification

This is a CCI [REDACTED] study in which dose modification is not permitted.

## 6.7. Continued access to study intervention after the end of the study

Not applicable.

## 6.8. Treatment of overdose

For this study, any dose of bepirovirsen greater than CCI mg within a 24-hour time period will be considered an overdose.

GSK does not recommend specific treatment for an overdose. In the event of an overdose, the investigator/treating physician should:

1. Contact the Medical Monitor immediately.
2. Closely monitor the participant for AE/SAE and laboratory abnormalities until the study intervention can no longer be detected systemically (at least 50 days).

Document the quantity of the excess dose as well as the duration of the overdosing in the eCRF).

**CONFIDENTIAL**219239  
Protocol

## **6.9. Prior and concomitant therapy**

Any medication or vaccine (including over-the-counter or prescription medicines, recreational drugs, vitamins, and/or herbal supplements) that the participant is receiving at the time of enrollment or receives during the study must be recorded along with:

- Reason for use
- Dates of administration including start and end dates
- Dosage information including dose and frequency

The medical monitor should be contacted if there are any questions regarding concomitant or prior therapy.

Participants must abstain from taking prescription or nonprescription drugs (including vitamins, recreational drugs, and dietary or herbal supplements) within 7 days (or 14 days if the drug is a potential enzyme inducer) or 5 half-lives (whichever is longer) before the start of study intervention until completion of the follow-up visit, unless, in the opinion of the investigator and sponsor, the medication will not interfere with the study.

Acetaminophen, at doses of  $\leq$ 2 grams/day, is permitted for use any time during the study. Other concomitant medications may be considered on a case-by-case basis by the investigator in consultation with the medical monitor, if required.

## **7. DISCONTINUATION OF STUDY INTERVENTION AND PARTICIPANT DISCONTINUATION/WITHDRAWAL-**

### **7.1. Discontinuation of study intervention**

Discontinuation of study intervention is not applicable in this study, as it is a single dose by design. Monitoring criteria are outlined in the section below.

#### **7.1.1. Liver chemistry monitoring criteria**

Liver chemistry stopping and increased monitoring criteria have been designed to assure participant safety and evaluate liver event aetiology. Although stopping criteria for continued dosing of study intervention are not applicable for single dose studies, if participants are found to have values consistent with usual stopping parameters, it is appropriate to institute evaluation and monitoring criteria according to standard GSK criteria. Therefore, liver function tests should be evaluated according to stopping criteria and safety follow-up procedures/tests as specified in [Appendix 6](#) should be instituted if defined parameters are reached.

For ALT values  $\geq$ 3xULN:

- See [Appendix 6](#)

**CONFIDENTIAL**219239  
Protocol

- if possible Hy's Law case: ALT  $\geq 3 \times \text{ULN}$  and total bilirubin  $\geq 2 \times \text{ULN}$  ( $>35\%$  direct) or INR  $> 1.5$ , report as an SAE

### 7.1.2. Hematological monitoring criteria

Platelet counts must be re-checked as soon as possible (with a new blood sample) if the platelet count is uninterpretable, below the LLN reference range for healthy participants, or the sample shows platelet clumping.

Monitoring criteria are shown in [Table 7](#)

Participants with platelet counts  $< 75 \times 10^9 / \text{L}$  will undergo further assessment including, but not necessarily limited to, anti-platelet antibodies. Monitor until platelet abnormalities resolve, stabilize, or return to within baseline values.

After the dose is administered, if a participant develops signs or symptoms of thrombocytopenia, obtain a platelet count as soon as possible.

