Participants are excluded from the study if any of the following criteria apply:

Medical Conditions
1. History or presence of cardiovascular, respiratory, hepatic, renal, gastrointestinal, endocrine, hematologic, or neurological disorders capable of significantly altering the absorption, metabolism, or elimination of drugs; constituting a risk when taking the study intervention or interfering with the interpretation of data.
2. Abnormal blood pressure as determined by the investigator.
3. Lymphoma, leukemia, or any malignancy within the past 5 years except for basal cell or squamous epithelial carcinomas of the skin that have been resected with no evidence of metastatic disease for 3 years.
4. Participants with signs or symptoms suggestive of COVID-19 (e.g., fever, cough) within 14 days of inpatient admission.
5. Participants with any other medical conditions which, in the judgement of the investigator and Medical Monitor, could jeopardize the integrity of the data derived from that participant or the safety of the participant.
6. Platelets $<140 \times 10^9 / \text{L}$ .
7. ALT $>1.5 \times \text{ULN}$
8. Total bilirubin $>1.5 \times \text{ULN}$ (isolated total bilirubin $>1.5 \times \text{ULN}$ is acceptable if total bilirubin is fractionated and direct bilirubin $<35\%$ ).
9. Current or chronic history of liver disease or known hepatic or biliary abnormalities (with the exception of Gilbert's syndrome or asymptomatic gallstones).
10. QTcF $>450$ msec.
Prior/Concomitant Therapy
11. Past, current or intended use of over-the-counter or prescription medication [including herbal medications] within 7 days or 5 half-lives (whichever is longer) before dosing [Specific medications listed in Section 6.9 of the protocol may be allowed].
12. Current or prior use of creatine-containing supplements and intended use up to 50 days post-dosing.
13. Prior use of immunosuppressive drugs within 3 months before dosing or interferon within 12 months before dosing.
14. Prior treatment with any oligonucleotide or small interfering RNA (siRNA) within 12 months before dosing.

**CONFIDENTIAL**219239  
Protocol

Prior/Concurrent Clinical Study Experience
15. Loss of blood or blood products in excess of 500 mL within any 3-month period during the study.
16. Exposure to more than 4 new chemical entities within 12 months prior to the first dosing day.

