**Table 7 Hematological Monitoring Criteria**

Platelet Count Value	Monitoring
$75 \times 10^9 / \text{L} \leq \text{platelets} < 100 \times 10^9 / \text{L}$	Monitor weekly until $\geq 100 \times 10^9 / \text{L}$
$50 \times 10^9 / \text{L} \leq \text{platelets} < 75 \times 10^9 / \text{L}$	Assess anti-platelet antibodies Monitor every 2 to 3 days until 3 successive measurements $\geq 75 \times 10^9 / \text{L}$ , then weekly until $\geq 100 \times 10^9 / \text{L}$
$< 50 \times 10^9 / \text{L}$	Assess anti-platelet antibodies Monitor daily until $> 25 \times 10^9 / \text{L}$ , then every 2 to 3 days until 3 successive measurements $\geq 75 \times 10^9 / \text{L}$ , then weekly until $\geq 100 \times 10^9 / \text{L}$

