4.1.2. Baseline Definition

For all endpoints (except as noted in baseline definitions) the baseline value will be the latest pre-dose assessment with a non-missing value, including those from unscheduled visits. If time is not collected, Day 1 assessments are assumed to be taken prior to first dose and used as baseline.

For ECG and/or Vital Signs analyses, if the last, non-missing pre-dose values is measured in triplicate, then the subject level baseline is defined as the mean of the triplicate baseline assessments.

Blood pressure and pulse will be measured in triplicate before dosing, single measurements after dosing. Single temperature and respiratory rate measurements will be measured at all time points. When measurement is repeated at the same time point then the mean will be used.

Unless otherwise stated, if baseline data is missing no derivation will be performed and baseline will be set to missing.

Baseline of serum creatinine is defined as the mean of all pre-dose values, from screening to Day 1 pre-dose assessment.

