4.5.2.3. Monitoring Event Reporting

Liver monitoring and stopping event reporting will be summarized and listed. The Liver monitoring and stopping criteria are described in the protocol Section 7.1.1.

Haematological monitoring will be summarized and listed based on laboratory parameters (platelet count and anti-platelet antibodies). The haematological monitoring criteria are described in the protocol Section 7.1.2.

Data for potential Drug induced kidney injury (renal) monitoring events will be captured in the eCRF; they will be summarized. The kidney injury monitoring criteria are described in the protocol Section 7.1.3.

Data for potential drug induced vascular injury and complement monitoring will be captured in the eCRF; they will be summarized. The drug induced vascular injury and complement monitoring criteria are described in the protocol Section 7.1.4.

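### After a platelet count below 75 x10^9/L, the Section 7.1.2 text lets monitoring end on stabilization, but Table 7 continues it until at least 100 x10^9/L, and the protocol does not say which governs

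*Protocol*

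**What the plan says.** Protocol Section 7.1.2 covers platelet monitoring after the dose. It introduces its table with the words "Monitoring criteria are shown in" Table 7. It then requires further assessment, including anti-platelet antibodies, for counts below 75 x10^9/L. The next sentence gives an end rule: "Monitor until platelet abnormalities resolve, stabilize, or return to within baseline values". It names no count, and neither resolution nor stabilization is defined.

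Table 7 gives a different end rule in its two rows below 75 x10^9/L:

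- **50 to below 75:** "Monitor every 2 to 3 days until 3 successive measurements" of at least 75 x10^9/L, then weekly until at least 100 x10^9/L.
- **Below 50:** a daily step first, then the same sequence, again ending at 100 x10^9/L.

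Neither row has an exit for stabilization.

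Protocol Section 8.4.4.3 lists thrombocytopenia among the adverse events of special interest and names Section 7.1.2 as its monitoring strategy. SAP Section 4.5.2.3 refers back to the same place: "The haematological monitoring criteria are described in the protocol Section 7.1.2". None of these passages ranks the text against the table.

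**The concern.** The two passages cover the same participants and set different conditions for stopping. A site following the text may stop once the count is steady. A site following the table may not stop until the count reaches 100 x10^9/L. Both sites would be complying with the protocol.

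What is at stake is uniform safety follow-up for an event that Section 8.4.4.3 itself describes as ranging up to fatal bleeding. How long a low count is watched, and how closely, should not depend on which paragraph of one section the site applies.

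**Working it through.** No sample size, power or error rate is involved, and the plan states no figure to reproduce. The check sets the two end rules side by side.

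**Inputs.** The text rule comes from Section 7.1.2, the table rule from the two Table 7 rows below 75 x10^9/L, and the scheduled haematology days from footnote 4 of Table 2. The counts below are illustrative, in units of 10^9/L.

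| Course after a fall below 75 | Section 7.1.2 text | Table 7 |
|---|---|---|
| Falls to 60, then steady at 85 | May end: stabilized | Continues weekly, because 85 is below 100 |
| Falls to 60, then steady between 50 and 75 | May end: stabilized, no minimum count given | Stays on the 2-to-3-day step, because three successive values of at least 75 are not reached |
| Recovers and is steady at 100 or above | May end: stabilized | Ends |

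The rules part in the first two rows and agree in the third. The disagreement comes entirely from stabilization being sufficient in the text and absent from the table.

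**Size of the gap in sampling.** Take a participant on the weekly step at Day 15 whose count stays on a plateau below 100 and out of the normal range.

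- Table 2 then gives haematology on Day 29, on Day 43 if the Day 29 result is still out of range, and on Day 64. The intervals are 29 - 15 = 14, 43 - 29 = 14 and 64 - 43 = 21 days.
- Against a 7-day interval these are 14/7 = 2, 14/7 = 2 and 21/7 = 3 times as long.
- From Day 15 to Day 64 there are 64 - 15 = 49 days. Weekly counting gives 49/7 = 7 counts, and the schedule gives 3. The difference is 7 - 3 = 4 counts, at about Days 22, 36, 50 and 57.

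This is the largest difference for that participant if nothing else prompts a sample. Section 8.3.5 may prompt more, as discussed under the objection. Table 7 also has no end date, so its weekly counts would run past Day 64 if the plateau persisted.

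**The case against.** The best defence is that the passages can be read together. The table would set how often to sample in each count band, and the sentence would set the general closing condition. The protocol uses that pairing elsewhere. Renal monitoring in Section 7.1.3 is weekly with much the same closing words, and liver monitoring in Appendix 6 is weekly or twice weekly with much the same closing words. Section 10.3.4.5 also lets follow-up of special-interest events end once they have stabilized. A different defence is that a site would treat the table as the specific rule and the sentence as general wording.

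Both readings are reasonable, but they give opposite answers for a plateau below 100. In the renal and liver sections the closing words do not compete with a numeric end point. In Table 7 each row carries its own. The protocol does not choose between the readings, so the conflict stands.

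Other parts of the defence do limit the point:

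- **Platelet follow-up does not simply cease.** A reader might infer that stopping under Section 7.1.2 ends it altogether. The documents do not support that. Section 8.3.5 has clinically significant abnormal values repeated until they are normal, back to baseline or no longer judged clinically significant, and Table 2 repeats out-of-range results.
- **The event should be uncommon.** Section 2.3.1 describes the risks at this dose as of low likelihood, and the conflict needs a particular course after a marked fall.
- **No effect on the analysis is shown.** A reader might infer that the SAP outputs would be distorted. SAP Section 4.5.2.3 bases its haematological monitoring summaries on platelet counts and anti-platelet antibodies, and Section 4.5.2.2 uses worst-case post-baseline grades. No visible text analyses how long monitoring lasted. Recovery is recorded as the investigator's outcome assessment under protocol Section 10.3.4.4.

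A reader might also infer a conflict in the opposite direction: that a recovery to between 100 and 139 ends monitoring under the table but not under the text, because exclusion criterion 6 bars counts below 140 and such a value is therefore not back to baseline. This fails because return to baseline is only one of three alternatives. A count steady at 120, or judged resolved there, meets the text as well as the table. At most the text might run longer while a count above 100 is still rising. Nor does exclusion 6 fix the baseline. The SAP states that "the baseline value will be the latest pre-dose assessment with a non-missing value, including those from unscheduled visits", and haematology is drawn again shortly before dosing, so baseline is normally but not necessarily at least 140.

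**Conclusion.** The concern holds in one direction. After a fall below 75 x10^9/L, a plateau below 100 x10^9/L may end monitoring under the Section 7.1.2 text but not under Table 7, and nothing in the protocol settles which applies. Participants with the same counts could therefore be followed differently for an event of special interest.

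The conclusion rests on reading the three conditions as alternatives, as the wording has it, and on applying the sentence to counts below 75, which its position supports. Whether it also reaches participants whose lowest count is between 75 and 100 depends on how it is read, and the point does not rely on that.

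The effect is confined to consistency of safety follow-up in what should be few participants. The primary and secondary PK endpoints are untouched. The issue is still worth correcting, because these are two explicit safety rules that disagree, not a missing detail.

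**What to change.** Amend the end-of-monitoring sentence in protocol Section 7.1.2 so that it agrees with Table 7, or add a statement of which passage governs. If stabilization is meant to end monitoring, the table should say so. If it is not, the text should not offer it for these participants. Which end point is clinically right is for the sponsor's medical team to decide, and none is proposed here.

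The cost is one sentence and its inclusion in an amendment. It adds no assessment beyond those that one of the two passages already requires. The SAP needs no change, because it refers to Section 7.1.2 and would follow the reconciled rule.
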